4.3 SCREEN FAILURES

Potential participant HbA1c less than 6.0 or greater than 6.5% or meets any of the above referenced inclusion criteria.

4.4 STRATEGIES FOR RECRUITMENT AND RETENTION

Recruitment from four primary care clinics in the AL Black Belt will be in a manner similar to that used for our previous trials implemented in primary care, including our ongoing Southeastern Collaboration to Improve Blood Pressure" in which we have currently enrolled 660 patients from 31 primary care clinics in the Black Belt. We will begin by conducting chart reviews and send direct mailings to practice lists of potentially eligible patients that include opt-out postcards providing a brief study description and contact information followed by recruitment phone calls after 2 weeks. In our experience, this strategy yields by far the highest return. We will also place flyers in accessible, high-traffic areas (e.g., waiting

room, exam rooms) and provide practice staff with simple and brief forms to refer patients. We will also conduct periodic 'lunch and learn' seminars for practice staff to facilitate referrals. Given our significant experience recruiting from primary care, the high prevalence of pre-diabetes and obesity in the rural south, and the strong interest in weight management programs in general, we do not anticipate difficulty recruiting and enrolling the required number of participants. The text of all announcements and advertisements and all recruitment methods will have IRB approval prior to use. Solicitation of information from candidates will be conducted in a HIPAA-compliant manner. A trained recruiter will follow up with the patient to assess their interest in participating and screen them for eligibility during a screening visit (SV) in which they will have a point-of-care A1c conducted and answer a screening questionnaire to determine their eligibility. Following the completion SV activities, if the patient is deemed eligible, he/she will provide written informed consent prior to participating in baseline measurements to formally enrolled in the study at the baseline visit. Patients who participate in the SV activities will not be considered enrolled in the study until they have provided informed consent and completed baseline measurements. Patients may choose to complete the baseline measurements at the SV or schedule an appointment to conduct baseline measurements.

A variety of approaches will be used to retain patients. Based on our experience, we understand the importance of creating a pleasant clinic environment and friendly and welcoming staff presence. We are also very clear from the initial screening session onward about what we expect from patients and what they can expect from us, as keeping patients well informed enhances adherence to the intervention and test schedules. All participants receive a tablet device (similar to Amazon Fire valued at up to \$90) and upon study completion, a body weight scale (valued at 425). Finally, a total of \$150/patient is budgeted for incentives related to the provision of outcome measures. All patients will be paid at the completion of each assessment visit (\$40 at baseline, \$50 at 6-months and \$60 at 12-months).

5 RANDOMIZATION/BLINDING

Randomization. This is a cluster-randomized trial, and enrolled patients at a given clinic will receive the intervention assigned to their clinic. A total of 4 primary care clinics in rural Alabama will be randomized to either 1) Receive lifestyle modification alone (DPP) or 2) Receive lifestyle modification with metformin therapy recommendations (DPP-recommendations).

Blinding. Given that this trial is a small pilot randomized at the clinic level and the interventions are very distinct, patients will know their group assignment, as will clinic staff, CHWs, and research staff that are involved in delivering the intervention.

6 INTERVENTION METHODS

6.1 OVERVIEW OF INTEVENTION ARMS

The overall study design of Prevent T2 trial is a cluster-randomized, two-arm controlled trial with a total of 4 primary care clinics in rural Alabama will be randomized to either 1) Receive lifestyle modification alone (DPP) or 2) Receive lifestyle modification with metformin therapy recommendations (DPP-recommendations). Study staff will work with practices to recruit 25 participants from each clinic for a total 100 participants.

6.1.1 DESCRIPTION OF LIFESTYLE INTERVENTION ARM

All enrolled participants will receive lifestyle modification intervention. Participants will receive Diabetes Prevention Program Curriculum educational materials related to PreventT2 intervention that include evidence-based recommendations for dietary modification, increased moderate-intensity physical activity, and behavioral strategies designed to support these lifestyle changes to promote healthy weight loss to delay or prevent the development of type 2 diabetes.

Program materials were accessed and printed for study use from public sources:

<https://www.cdc.gov/diabetes/prevention/resources/curriculum.html> The CDC Diabetes Prevention Program Curriculum (CDC DPP Curriculum) is based on the curriculum from the Diabetes Prevention Program (DPP) research study supported by the National Institutes of Health, National Institute of Diabetes and Digestive and Kidney Disease (U01-DK48489). All participants will also receive a RM body weight scale, the Ideal Life Body Weight Scale. Participants will be asked to: (1) keep the scale in their bedroom, (2) weigh daily at the same time in light clothing, and (3) view and log their daily weight checks. Study staff will review with participants how to set-up and use the scale. Participants will receive a binder and additional program materials over the course of the 12-month program. Trained health educators will deliver the DPP intervention to all participants on a rolling schedule. The DPP is an evidence-based intensive lifestyle modification program to prevent or delay type 2 diabetes that asks that participants attend 26 group sessions over 12 months. Peer coaches will facilitate the delivery of the DPP. Participants are asked to attend 16 weekly group sessions, 4 bi-monthly sessions, and 6 monthly sessions over the course of 12 months. Group sessions will be held via Zoom.

Peer Coaches for this trial will be hired and supervised by community partner whose primary mission is to train, employ, and deploy CHWs, ConnectionHealth. Peer Coaches will complete over 20 hours of training in the peer coach study protocol. Study participants will be matched with a Peer Coach who will conduct brief scheduled telephone contacts with each participant over the course of 12 months to provide support for behavior modification and help participants problem solve to overcome barriers. The scheduled contacts with peer coaches will take place 1-10 days before each scheduled DPP group session. Peer coaches will facilitate make-up sessions for missed group session. Make-up sessions may be viewed on a private YouTube channel or at scheduled visit with the peer coach using a tablet.

6.1.2 DESCRIPTION OF LIFESTYLE INTERVENTION WITH METFORMIN THERAPY RECOMMENDATIONS ARM

Lifestyle intervention program (telehealth + peer coach) with metformin therapy recommendations (DPP-recommendations): Participants will receive the same lifestyle intervention as those in the DPP condition described above. In addition to the lifestyle intervention, they will receive a recommendation for metformin therapy for prevention of type 2 diabetes. Primary care providers at the practices randomized to the DPP-recommendations condition will attend an orientation session and evidence-based materials about low-dose metformin therapy recommendations for patients with pre-diabetes to prevent or delay the onset of type 2 diabetes. At the baseline assessment, study staff will provide participants with the patient education handout on “Understanding Metformin for Pre-diabetes” that details using metformin for prevention of type 2 diabetes. At the same time, the participant’s primary care provider will receive a recommendation to provide their patient with a prescription for Metformin for diabetes prevention. The communication between study staff and PCPs will be developed and

tailored to fit the work flow of each clinic. As described in the inclusion/exclusion criteria, participants without a charted eGFR or an eGFR<60 within the last 6-months will be excluded from the study.

7 DATA COLLECTION PROCEDURES

Data will be collected at chart review (CR), a screening visit (SV), a baseline visit (BV), and at 6- and 12-month visits. The physical measurements that will be made as well as the questionnaires to be used are described below. All physical measurements will be recorded on the Measurements Form.

Chart Review and Screening Visit. Chart reviews will be conducted, and direct mailings will be sent to practice lists of potentially eligible patients that include opt-out postcards providing a brief study description and contact information followed by recruitment phone calls after 2 weeks to pre-screen patient for study eligibility. If eligible and interested, potential participants are scheduled for a Screening Visit (SV). A trained recruiter will assess patient interest in participating and screen them for eligibility during a screening visit (SV) in which they will have a point-of-care A1c conducted and answer a screening questionnaire to determine their eligibility. Following the completion SV activities, if the patient is deemed eligible, he/she will provide written informed consent prior to participating in baseline measurements to formally enrolled in the study at the baseline visit. Patients who participate in the SV activities will not be considered enrolled in the study until they have provided informed consent and completed baseline measurements. Patients may choose to complete the baseline measurements at the SV or schedule an appointment to conduct baseline measurements.

Finger-stick Blood Sample

Finger-stick blood samples will be used to measure hemoglobin A1c using a validated Bayer A1C Now+ point-of-care device at screening, month 6 and month 12 visits. The Bayer A1C Now+ is a small, portable analyzer that requires only a single drop of blood from a finger stick and eliminates the anxiety of a venipuncture. The research staff will clean the patient's fingertip with an alcohol wipe and obtain a drop of blood using a lancet. The blood is collected via specific tube and transferred to the A1C Now+ cassette. The results will be available in less than five minutes, and will be entered on the Measurement Form (see Appendix A) and data-entered by the research staff. Results will be entered onto the Health Report to be provided to the patient.

Baseline Measurements. After individuals have been recruited and screened, eligible patients will be invited to enroll and complete baseline assessments. This visit will include completing informed consent to participate in the study and completion of surveys. Baseline assessments will be conducted by trained recruiter at the patient's primary care clinic. Completion of the baseline assessment will take approximately 30 minutes to 60 minutes. Surveys may be completed in-person during the visit or at a later time over the phone. Upon completion of baseline assessments, they will receive specific information and materials relevant to the condition to which they have been assigned (described above). Study personnel will review these materials with participants during this study visit. It is anticipated that the review of intervention procedures and materials will take approximately 30 minutes to 60 minutes. Follow-up assessments will be conducted in a similar manner as described in bullet below.

Weight

Weight is the primary outcome for this study and will be measured with the patient in light indoor clothes without shoes to the nearest 0.1 kg using a digital scale at each assessment visit. Patients will be

instructed to stand still in the middle of the scale with head erect and eyes looking straight ahead. After the weight is recorded, the patient will step off of the scale and the research assistant will set the scale to zero, then repeat and record the second weight measurement. If the two readings differ by more than 0.5 kg, a third measurement will be obtained. The closest two measurements will be averaged for analysis. The accuracy of the scales will be checked at scheduled monitoring visits using standard weights. Weight will be measured at the baseline visit, and at the 6 and 12 month assessment visits.

Height

Height will be measured at the screening visit and the baseline visit using a portable stadiometer. The patient will be asked to remove their shoes and have their heels, buttocks and upper part of the back remain in contact with the stadiometer with their arms hanging naturally at their side. The patient is asked to inhale and hold their breath, while the technician lightly applies traction to the patient's head in order to maintain alignment with the Frankfort Plane. The slide is lowered until it reaches the vertex of the skull and the reading from the indicator is recorded to the nearest 0.1 centimeter. This process will be repeated, and if the two readings differ by more than 0.5 cm, a third measurement will be obtained. The closest two measurements will be averaged for analysis. Calibration of the portable stadiometer is not required, however the accuracy of the stadiometer will be checked at scheduled monitoring visits against a standard meter stick. It is not necessary for the stadiometer to be calibrated once all Baseline Visits are completed as height is not measured at follow-up measurement visits.

Questionnaires

All questionnaires will be interviewer administered and data-entered by research staff. Paper questionnaires will be used in the event of power or other equipment failure.

Baseline Demographic and Health History Questionnaire

A self-report demographic and health history questionnaire asks the patients about their age, sex, race/ethnicity, use of tobacco and alcohol, health insurance status, income and employment, education level, history of chronic diseases, and cellular phone ownership and internet use.

Change in Health History Questionnaire

A self-report questionnaire captures changes in health outcomes that have occurred across the 6 months of the intervention. This questionnaire is administered at the 6 and 12 assessment visits.

Patient-reported Quality of Life

PROMIS: Global Health, Physical Health, Mental Health, Physical Function, Social Isolation

PROMIS® stands for the Patient Reported Outcomes Measurement Information System

(www.nihpromis.org), which is a system of highly reliable, precise measures of patient-reported health status for physical, mental, and social well-being. The PROMIS items were developed using a rigorous methodology funded by the National Institutes of Health (NIH) with a goal to develop valid, reliable, and standardized questionnaires or tools to measure patient-reported outcomes. A previous study has shown that among people with disabilities, health-related quality of life was significantly lower among the obese as measured by the PROMIS scales as compared to the non-obese. The PROMIS measures will be administered at baseline, and at the 6 and 12 visits.

Dietary Intake Questionnaire

A questionnaire that assesses fruit, vegetable and alcohol intake is administered at baseline and at the 6- and 12-month assessment visits. The questionnaire contains scales derived from several sources. A standard 6-item fruit and vegetable screener developed by the NCI and National 5 a Day Program

grantees asks how often fruit and vegetables were consumed in the past month. One question related to the frequency of alcohol intake (beer, wine, hard liquor) in the past 30 days.

Simple Physical Activity Questionnaire – SIMPAQ

Physical activity levels are measured at baseline and at the 6 and 12 month assessment visits using the SIMPAQ which asks questions related to physical activity performed over a representative 24-hour period from the previous 7 days. The SIMPAQ has acceptable reliability.

Perceived Competence: Maintaining a Healthy Diet and Exercising Regularly

The Perceived Competence Scale is designed to measure competence in different dimensions within lifestyle modification. For the purpose of this trial, only Maintaining a Healthy Diet and Exercising Regularly scales were administered at baseline, and at 6 and 12 month assessment visits.

Personal Health Questionnaire Depression Scale

Personal Health Questionnaire Depression Scale (PHQ8) is a screener designed to measure depressive symptoms in an adult population. PHQ8 consists of 8 items scored 4-point Likert scale. Higher scores indicate more depressive symptoms.

Perceived Stress Scale (PSS-4)

Perceived Stress Scale (PSS-4) is tool to evaluate control and confidence in handling stressful situations. The PSS-4 consists of 4 items scored on a 5-point Likert scale, with reverse coding for 2 items. Scores range from 0 to 16, with higher scores indicating higher levels of stress.

Follow-up Assessments. For follow-up assessments at month 6 and month 12, a trained staff will conduct measures of a point of care HbA1c, weight and surveys/questionnaires completed by participants. Patient-reported surveys/questionnaires may be completed in-person or over the phone prior to the in-person visit depending on participant preferences. For all in-person visits, telephone calls will be made to schedule these visits and provide reminders for upcoming visits. Reminder calls will occur 1-7 days prior to scheduled appointments.

Chart Review: Medical Record Data Collection

In addition to data collection of outcome measurements by the research staff, a chart review data collection effort will be done by utilizing the medical records at the participating clinics. For each of the participating patients in both arms, a retrospective chart review covering the period of the intervention will be done to abstract data on clinical variables of interest over the course of the intervention. The electronic medical records of the patients will be obtained, or in cases where electronic records are not available, paper medical records will be abstracted by hand and data-entered by research staff.

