The primary outcome measures include feasibility assessment and the measurement HbA1c and body weight at baseline, 6 months, and 12 months. Demographic characteristics will be collected at screening and baseline. Participants will be enrolled for one-year period. This is a pilot trial designed to test feasibility for a larger scale randomized clinical trial that will evaluate effectiveness of an innovative lifestyle intervention combined with metformin in for diabetes prevention.

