4.1 INCLUSION CRITERIA

- Age 19 (the age of adulthood in Alabama) to 65 years
- A1c (A1c) 6.0% to 6.4%
- Body mass index (BMI) 30-50 kg/m²
- Receives care at one of the 4 participating primary care clinics
- Resides in one location at least 5 days each week
- Telephone line or Wi-Fi internet connection or cellular signal in home
- Willing or able to partner with a Community Health Worker
- Willing to attend group sessions

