13 DATA ANALYSIS PLAN

Mixed models will be used to estimate the changes in outcomes by intervention with confidence intervals using practice as a random effect to account for clustering within practices. Secondary models will adjust for baseline values. In 2011, Katula et al. published 12-month results of randomized controlled trial comparing a community-based translation of a DPP lifestyle intervention conducted in a southern sample with usual care. Combined with data generated in our feasibility trial, this relevant study should further help inform our power assessments for a larger RCT. The change values observed in the control group in that project will serve as a reference for expected change in weight without any intervention and will be used to estimate the change due to the intervention.

Handling of Missing Data

Missing data are expected due to dropouts and missed visits. Weight loss is a subject-level variable and missing assessments would influence tests relative to treatment-by-time interactions. The primary analysis described above will employ restricted maximum likelihood using all data. No patients will be deleted from the analysis because of partial data. To assess the sensitivity of results, weight loss will be

analyzed using: 1) all patients irrespective of missing data to perform analysis of variance using mixed effects multi-level models with repeated measures; 2) only patients who have completed all assessment visits and have no missing data, to perform analysis of variance employing mixed effects multi-level models with repeated measures; 3) all patients, irrespective of missing data, to conduct analyses using mixed effects multi-level time trend models with random coefficients to capture individual time trends (does not require complete data across time); and 4) multiple imputation.

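### The only scheduled pre-treatment HbA1c is the screening reading that admitted the patient, so within-arm HbA1c change may include a shift due to selection alone

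*Combined protocol and SAP*

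**What the plan says.** HbA1c is a primary outcome alongside body weight (sections 1.1 and 3). Section 3 lists "the measurement HbA1c and body weight at baseline, 6 months, and 12 months". Section 7, under the finger-stick heading, schedules HbA1c with a "validated Bayer A1C Now+ point-of-care device at screening, month 6 and month 12 visits". Its description of the baseline visit says "This visit will include completing informed consent to participate in the study and completion of surveys" and mentions no HbA1c. Weight is treated differently: "Weight will be measured at the baseline visit, and at the 6 and 12 month assessment visits".

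The screening reading is the entry gate. At the screening visit "they will have a point-of-care A1c conducted and answer a screening questionnaire to determine their eligibility", and section 4.1 sets the window as "A1c (A1c) 6.0% to 6.4" percent.

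Section 13 states: "Mixed models will be used to estimate the changes in outcomes by intervention with confidence intervals". Adjustment for baseline values is left to secondary models. The outside control group used as a no-intervention reference is invoked for weight only. Chart abstraction (section 7) covers the intervention period and names no pre-treatment HbA1c.

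**The concern.** A point-of-care reading is true HbA1c plus device error and day-to-day variation. Admitting patients because one such reading fell in a narrow window keeps some whose error put them there. The follow-up readings pass through no such filter, so the mean can move between screening and month 12 even if nobody's true HbA1c changes.

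Two things are at stake. First, within-arm HbA1c change could be taken as an effect of the lifestyle programme. Both arms get that programme and no HbA1c reference without intervention is planned, so nothing in the design would reveal the artefact. Second, the pilot is meant to inform the design and power of a later study. A baseline confined to the entry window has an artificially small SD and a weakened correlation with follow-up.

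**Working it through.** **Schedule.** Section 3 gives baseline, 6 and 12 months. Section 7 gives screening, 6 and 12 months, and nothing at the baseline visit. No passage names another pre-treatment HbA1c or says which reading is the analysis baseline.

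**The plan's own figures.** Section 12 gives no HbA1c variance or precision. For weight it gives effective sizes of 40 and 33 per arm, with half-widths of ±0.28 to ±0.35 SD. Check: 50/1.24 = 40.3 and 40/1.19 = 33.6. Then 1.96/√33 = 0.34 (0.355 with the t quantile), while 0.28 corresponds to 1.96/√50 = 0.277, that is, to 50 patients without the design factor. These figures serve below only as a yardstick.

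**Inputs for the shift.** From the documents: entry window 6.0-6.4%. Assumed, because the documents do not give them: readings reported to 0.1 (so 5.95-6.45 before rounding), normal distributions, screened-pool mean 5.8-6.2% (6.3% also tried), true SD 0.3-0.4, and error SD (device plus day-to-day) 0.10-0.30.

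**Formula.** Reliability ρ = SD_true² / (SD_true² + SD_error²). Expected change with no treatment effect = -(1 - ρ) × (mean selected reading - pool mean).

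**Examples at pool mean 5.8%.**
- True SD 0.3, error 0.30: ρ = 0.09/0.18 = 0.50; -(0.50) × (6.158 - 5.8) = -0.18.
- True SD 0.3, error 0.20: ρ = 0.09/0.13 = 0.69; -(0.31) × (6.144 - 5.8) = -0.11.
- True SD 0.4, error 0.20: ρ = 0.16/0.20 = 0.80; -(0.20) × (6.162 - 5.8) = -0.07.

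**Simulated mean change, no true change (HbA1c points).**

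| Pool mean | SD 0.3, error 0.15 | SD 0.3, error 0.20 | SD 0.3, error 0.30 | SD 0.4, error 0.20 |
|---|---|---|---|---|
| 5.8 | -0.070 | -0.107 | -0.180 | -0.074 |
| 6.0 | -0.034 | -0.053 | -0.090 | -0.037 |
| 6.2 | 0.000 | 0.000 | -0.001 | 0.000 |
| 6.3 | +0.017 | +0.026 | +0.045 | +0.019 |

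In the 5.8% row, the largest shift is 0.180/0.375 = 0.48 SD of change and the last column is 0.074/0.273 = 0.27 SD. That is about the size of the half-width the plan quotes for weight.

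**Spread.** Over error SD 0.10-0.30, the screening SD among those selected is about 0.13-0.14, against 0.18-0.40 at follow-up. The screening-to-follow-up correlation is 0.18-0.67.

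**Between arms.** If both arms' screened pools are alike, the shifts cancel in expectation. If pool means differ by 0.1-0.2 points, roughly (1 - ρ) times that difference remains: 0.02-0.04 at ρ = 0.80 and 0.05-0.10 at ρ = 0.50. Adjusting for the screening value does not remove this remainder.

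**With a separate baseline reading.** The no-effect change is zero in every scenario (within 0.002), and the correlation with follow-up is 0.35-0.71. The SD of change rises slightly (0.273 to 0.285 at mean 5.8, true SD 0.4, error 0.20), so bias goes but the interval does not narrow. On the 5.8-6.2% grid, 3% to 26% of those selected would read 6.5% or more on the repeat.

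**The case against.** Sections 4.4 and 7 let patients complete baseline measurements at the screening visit, so baseline in section 3 may be shorthand for screening. That would ease the contradiction, but the text does not say so and the selection problem would remain.

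The endpoint in section 1.1 can be read as the month-12 value rather than change, section 7 calls weight the primary outcome, and section 13 already has baseline-adjusted models. This stands in part: the remedy largely promotes a model already planned. The main models still estimate change, however, and HbA1c is still named as a primary outcome.

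Three stronger readings are tempting and are not supported:
- *That HbA1c will show a spurious fall.* The window is two-sided. The shift is zero if the screened pool centres at 6.2% and upward above that. Chart review and a telephone pre-screen come before testing, so the pool may already lie near the window.
- *That the trial's comparison is biased.* Both arms use the same window. A residue arises only if the clinics' screened pools differ, which two clinics per arm cannot rule out but which nothing in the documents shows.
- *That the screening SD and correlation are useless for planning.* They would be the relevant inputs if the later trial kept the same window and screening baseline. The later study's stated main outcome is diabetes prevention, and HbA1c SD is not a named planning input.

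**Conclusion.** The concern holds in limited form. The schedule mismatch and the double use of the screening reading are plain from the text. Within-arm HbA1c change may include a shift due to selection. Under the assumptions above it is 0 to -0.18 points for pool means of 5.8-6.2%; at error SD 0.20 it is -0.07 to -0.11 at 5.8%, -0.04 to -0.05 at 6.0% and zero at 6.2%. It becomes a rise of up to 0.05 at 6.3%. Direction and size rest on device error and pool mean, neither of which the documents give. The narrowed screening SD appears in every scenario tried. A reader might infer that any observed HbA1c fall would be artefact. The documents do not support that either; they show only that the planned within-arm estimate could not separate the two.

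**What to change.** **(a) Wording only.**
- Reconcile sections 3 and 7, and state which reading is the HbA1c baseline.
- Make the between-arm difference in month-12 HbA1c, adjusted for that reading, the main HbA1c result. This moves the adjusted model from secondary to primary.
- State that within-arm change from the screening value includes regression to the mean and is not by itself evidence of a lifestyle effect.
- Use the screening SD and correlation for planning only if the later trial keeps the same window and screening baseline.

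**(b) Optional.** Carry out the baseline HbA1c that section 3 already lists, before intervention materials are handed over, and use it as the analysis baseline. The cost is one more finger-stick and cartridge for each of up to 100 patients. It removes the within-arm bias without narrowing the interval.

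If (b) is adopted, the sponsor must reconcile how a baseline reading outside the window, including 6.5% or more, is handled. The relevant text is section 4.2 (6.5% or more is an exclusion), section 4.3 ("Potential participant HbA1c less than 6.0 or greater than 6.5" percent is a screen failure, which does not match 4.1 and 4.2 at 6.5%), sections 4.4 and 7 (no one is enrolled until baseline measurements are complete), and the A1c alert value in the data quality and safety review plan. No eligibility rule is proposed here.

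### Baseline questionnaires may be taken by phone after the visit at which arm-specific materials are reviewed, so some baseline questionnaire scores can be recorded after first exposure

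*Combined protocol and SAP*

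**What the plan says.** Four statements in Section 7 and two in Section 6.1.2 bear on the order of events.

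- Section 7, Baseline Measurements, on survey timing: "Surveys may be completed in-person during the visit or at a later time over the phone". No window or latest date is given.
- The same paragraph, on when materials are released: "Upon completion of baseline assessments, they will receive specific information and materials relevant to the condition to which they have been assigned (described above".
- The same paragraph, on when they are discussed: "Study personnel will review these materials with participants during this study visit". The review is expected to last 30 to 60 minutes.
- Section 6.1.2, metformin-recommendation arm only: "At the baseline assessment, study staff will provide participants with the patient education handout on" metformin for prediabetes. It continues: "At the same time, the participant’s primary care provider will receive a recommendation to provide their patient with a prescription for Metformin for diabetes prevention".
- Section 7, Follow-up Assessments, on questionnaires at months 6 and 12: these "may be completed in-person or over the phone prior to the in-person visit depending on participant preferences".

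Section 7 (Chart Review and Screening Visit) also states that patients "will not be considered enrolled in the study until they have provided informed consent and completed baseline measurements".

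**The concern.** A baseline score should describe the participant before the programme touches them. Here a participant may attend the baseline visit, go through the arm's materials with staff, and answer the baseline questionnaires by phone on some later day. Several of those questionnaires ask about what the programme is meant to change: diet, physical activity, and confidence in managing both. On the last, the protocol says: "The Perceived Competence Scale is designed to measure competence in different dimensions within lifestyle modification". If a score has already moved when it is recorded as baseline, the change measured from it at months 6 and 12 is wrong by that amount.

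Section 13 models changes in outcomes by arm and adjusts for baseline in secondary models, so baseline values enter both. Section 3 says the pilot is to inform the design and power of a larger trial, so a distorted change estimate for a behavioural measure could be carried forward.

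**Working it through.** The plan gives no figure on this point, so there is none to reproduce. The check is one of order, followed by an illustration of size.

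**1. Order of events at baseline.** Consider a participant who uses the phone option after the visit.

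- The survey sentence places the survey after the visit.
- The review sentence places the materials review within the visit. The review therefore precedes the survey.
- The release sentence places the materials after baseline assessments are complete. The paragraph lists completion of surveys as part of the baseline visit, so surveys count as baseline assessments. The survey should therefore precede the review.

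The second and third results contradict each other. Either the materials come first, or the review does not take place at that visit. The protocol does not say which gives way.

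**2. Does the enrolment rule settle it?** No. It makes enrolment wait for completed baseline measurements, but it does not name surveys. Even if surveys are included, it governs enrolment status, not the release of materials.

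**3. What can come before a late survey?**

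- Both arms: the materials review.
- Metformin-recommendation arm: also the handout and the recommendation to the provider, which Section 6.1.2 ties to the baseline assessment.
- Coach calls and group sessions: Section 6.1.1 describes rolling delivery, with coach contacts 1–10 days before each session. With no survey window, nothing prevents a survey after the first of these. The documents do not say that this will happen.

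**4. Which measures are exposed?**

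| Measure | Position |
|---|---|
| SIMPAQ | Recalls the previous 7 days. A survey a week or more after the visit can have its whole recall period after the review. |
| Fruit and vegetable screener | Recalls the past month. At one week, about 23 of 30 days (30 − 7) still precede the visit. |
| Perceived Competence, PROMIS | Given at baseline; the protocol states no recall period. |
| PHQ-8, PSS-4 | Exposed only if given at baseline; their timing is not stated. |
| Weight | Measured in person at the baseline visit; not exposed. |
| HbA1c | Finger-stick at screening; not exposed. |

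**5. Size, for illustration only.** Let *f* be the share of baseline surveys done after the review, and *s* the shift in a late score, in SD, in the direction of improvement. Neither is in the documents.

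Bias in an arm's mean change = −(*f* × *s*)

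| *f* (assumed) | *s* = 0.1 | *s* = 0.2 | *s* = 0.3 |
|---|---|---|---|
| 10% | 0.01 | 0.02 | 0.03 |
| 25% | 0.025 | 0.05 | 0.075 |
| 50% | 0.05 | 0.10 | 0.15 |
| 100% | 0.10 | 0.20 | 0.30 |

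The entries are absolute values in SD. The arm contrast is biased only by the difference in *f* × *s* between arms. If the products are equal, the bias is zero. With *f* at 25–50% and *s* at 0.1–0.3, the most it can reach is 0.15 − 0.025 = 0.125 SD, and nothing in the documents points to that extreme.

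For scale, Section 12 states 95% confidence limits for change in body weight of ±0.28 to ±0.35 SD. That is for weight rather than questionnaires, so it is only a rough yardstick.

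**The case against.** The best reply is that the plan already states the right order: assessments first, materials second. On this reading the phone sentence is loose drafting, not a plan to collect baseline late. Section 10.1 refers to a written manual of procedures for screening, and Section 8 to standardized measurement protocols; a survey window may exist in documents not available here. The first part stands as a description of intent. It does not remove the problem, because the phone sentence permits what that order rules out, and the protocol does not resolve the conflict.

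Several limits on the size also stand. Long recall periods dilute a short delay. The lifestyle programme is the same in both arms, so much of any shift may cancel in the comparison. No questionnaire is named as an endpoint in the synopsis or singled out in Section 13.

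A reader might go further in several ways that the documents do not support:

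- **Loss of 10–20% of the true change.** This needs, for example, 20–40% late surveys with half the eventual change already present (0.2 × 0.5 = 10%; 0.4 × 0.5 = 20%). Half of a 6- or 12-month change is implausible after a short delay and one review session.
- **A false arm difference because phone use clusters by clinic.** With two clinics per arm this could happen, but nothing in the documents says that phone use will differ between clinics.
- **Participants go home with the scale and the curriculum.** Section 6.1.1 gives no hand-over date for the scale and spreads the binder and programme materials over the 12 months. Only the metformin handout is named as given at the baseline assessment.
- **Late surveys are the ones answered with the arm known.** Assignment is by clinic and open (Section 5), so in-person respondents may know it too. The materials review is an added exposure.
- **Baseline is deliberately ordered opposite to follow-up.** The follow-up text puts phone surveys before the visit. The baseline text sets no such limit, but it does not require surveys to follow the materials.

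**Conclusion.** The point holds as an unreconciled conflict within Section 7, with Section 6.1.2 adding arm-specific exposure. As written, some baseline values of PROMIS, diet, SIMPAQ and Perceived Competence, and of PHQ-8 and PSS-4 if given at baseline, can be recorded after the materials review.

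The likely effect is to shrink within-arm change in those measures. That direction assumes that early exposure moves scores the same way as the later programme. The amount cannot be known from the documents. At 25–50% late and a shift of 0.1–0.3 SD, both assumed, it is about 0.025–0.15 SD within arm. The effect on the arm comparison is probably smaller.

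A reader might infer that the trial's main results are at risk. They are not: weight and HbA1c, the primary clinical outcomes, are unaffected. The change is worth making because it is cheap and protects the questionnaire results.

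**What to change.** In Section 7, Baseline Measurements:

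1. Require all baseline surveys, in person or by phone, to be completed after consent, before any arm-specific material is given or reviewed, and before the first coach contact or group session. Where surveys will be done by phone, hold the materials review until they are finished.
2. Reconcile this order with the timing in Section 6.1.2 of the metformin handout and the recommendation to the provider.
3. Record the date and mode of every baseline survey.
4. Flag any survey done after the review. In Section 13, add a sensitivity analysis that repeats the questionnaire change analyses without those baseline values.

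Setting every late survey to missing in the main analysis is a harsher alternative and is debatable in a pilot of up to 100 participants; flagging keeps the data.

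The cost is a few sentences of text, the recording of date and mode, and one added sensitivity analysis. The practical downside is that for some participants the materials review moves to a later contact. The phone option is kept. If some surveys have already been done late, existing dates, where recorded, would allow them to be flagged.
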